8.3. Other Secondary Efficacy Analysis

The other secondary efficacy endpoints are summarized using OLE baseline, except for WI-NRS which will be summarized at both primary and OLE baseline. These are summarized as discussed in Section 8 and include the following:

- Change and percent change in Scalpdex total score as observed over time.
- Change and percent change in Overall Assessment of Erythema score
- Change and percent change in Overall Assessment of Scaling score
- Achievement of an Overall Assessment of Erythema (0-3 scale) score of 0 or 1 plus a 2-grade improvement from Baseline as observed over time.
- Achievement of an Overall Assessment of Scaling (0-3 scale) score of 0 or 1 plus a 2-grade improvement from Baseline as observed over time.

- Achievement of an Overall Assessment of Erythema (0-3 scale) score of 0 as observed over time.
- Achievement of an Overall Assessment of Scaling (0-3 scale) score of 0 as observed over time.
- Change and percent change from baseline in % BSA affected by disease as observed over time.
- Change and percent change in WI-NRS as observed over time.
- In subjects with a Baseline WI-NRS pruritus score of ≥ 4 , achievement of a ≥ 4 -point improvement from Baseline in WI-NRS pruritus score as observed over time.
- Achievement of itch-free state which is defined as WI-NRS of 0 or 1

Scalpdex questionnaire consists of 23 questions which are categorized into emotions, symptoms, and functioning scales. The scale scores and total score are calculated as described in the Section 6.1.7. Observed, change, and percent change from baseline for Scalpdex scale scores along with total score are summarized descriptively.

Observed, change, and percent change from baseline for WI-NRS and % BSA (total) affected by disease will be summarized descriptively.

In subjects with WI-NRS pruritus score ≥ 4 at baseline (primary and OLE), achievement of a 4-point reduction in WI-NRS pruritus score at each scheduled visit will be summarized. The number and percentage of subjects for each scale score will be summarized for OLE baseline.

The number and percentage of subjects who achieve Overall Assessment of Erythema Success, Overall Assessment of Scaling Success, Erythema score of 0, and Scaling score of 0 will be tabulated at each scheduled visit. In addition, categorical summaries (number and percentage of subjects) in each category will be summarized for Erythema and Scaling.

9. Safety and Tolerability Analysis

Safety will be evaluated from reported AEs, local tolerability assessments, changes in clinical laboratory values, changes in vital signs/weight, C-SSRS, PHQ-8/modified PHQ-A, and CDI-2 results.

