7.1.1. Baseline Definition

For subjects in Cohort 1, the baseline value for safety and efficacy parameters will be defined as the last observation prior to the first dose of ARQ-154 foam 0.3% in either the prior ARQ-154 study or this study (See [Section 7.2.1](#) for the definition of a treatment emergent event).

Additional analyses will be performed where the baseline value for subjects in Cohort 1 is defined as the last observation prior to the first dose of ARQ-154 foam 0.3% in this study. For the purpose of these latter analyses, study procedures will not be repeated; the information from the prior ARQ-154 study final visit will be carried over to the Day 1 visit for this study.

For subjects in Cohort 2, baseline values for efficacy and safety will be defined as the last observation prior to the first dose of ARQ-154 foam 0.3% in this study.

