6.1. Statistical Definitions and Algorithms

6.1.1. Baseline

There are three baseline definitions for the analyses:

- Primary baseline is defined as the last observation before the first dose of roflumilast foam 0.3% in either ARQ-154 parent study or this study for subjects administered vehicle previously.
- Open-label baseline (OLE baseline) is defined the last observation before the first dose of roflumilast foam 0.3% in this study. For subjects in Cohort 1 who choose to enroll in this study, study procedures will not be repeated; study sites will carry over the information from the prior ARQ-154 study to the Day 1 visit for this study. For subjects in Cohort 2 Group 4, the definition for Primary and OLE baseline is the same.
- Safety baseline is defined as primary baseline for Cohort 1 Group 1, and OLE baseline for Cohort 2 Group 3 and Group 4.

The following table described the baseline used in the analysis:

Cohort Groups	Prior therapy, medical history	Demog and Efficacy Analysis	Safety Analysis for AE, PHQ8, PHQ-A, Prior and Concomitant medications	Safety Analysis for lab, vital signs and tolerability assessments
Cohort 1 Group 1	OLE baseline	Primary baseline and OLE baseline	OLE baseline	Primary baseline
Cohort 2 Group 3	OLE baseline	Primary baseline and OLE baseline	OLE baseline	OLE baseline
Cohort 2 Group 4	OLE baseline	Primary baseline and OLE baseline	OLE baseline	OLE baseline
Cohort 2 Total	OLE baseline	Primary baseline and OLE baseline	OLE baseline	OLE baseline

Overall	OLE baseline	Primary baseline and OLE baseline	OLE baseline	Safety baseline of roflumilast foam 0.3% in this study for subjects in the safety analysis population. For subjects in Cohort 2 Group 4, the definition for Primary and OLE Baselines is the same
----------------	--------------	-----------------------------------	--------------	---

Baseline values will most commonly be from Day 1.

For subject tolerability assessments, baseline is derived as the last non-missing measurement taken on the day of first application of study drug.

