6.1.7. Derived Variables

- **IGA success** = IGA of “completely clear” or “almost clear” plus a 2-grade improvement from Baseline. For IGA success analysis, the subjects who achieved IGA of 0 or 1 at baseline will be excluded from the analysis.
- **Erythema success** = Erythema score of 0 or 1 plus a 2-grade improvement from Baseline as observed over time. For erythema success analysis, the subjects who achieved erythema score of 0 or 1 at baseline will be excluded from the analysis.
- **Scaling success** = Scaling score of 0 or 1 plus a 2-grade improvement from Baseline as observed over time. For scaling success analysis, the subjects who achieved scaling score of 0 or 1 at baseline will be excluded from the analysis.
- **Compliance** = number of applications divided by the expected number of investigational product (IP) applications for each subject. Compliance will be calculated using drug accountability data over the entire treatment period for each subject, up to treatment completion or discontinuation.
- **Number of expected IP applications** = calculated as last treatment date - first treatment date + 1. Excluding treatment-free interval time (defined in this section).
- **Number of IP applications** = number of expected IP applications – missed IP applications as collected in the CRF. Missed IP applications will not be taken into consideration in determining number of IP applications if the reason for missing dose is per investigator confirmation of clear.

- **Days on IP** = last date of IP application – first date of IP application +1. Subjects that stop taking IP per investigator confirmation of clear will be excluded from this calculation.
- **Treatment Gap** = This will be calculated for subjects belonging to Cohort 2 Group 3 that rolled into the extension study (ARQ-154-214) with a gap. This is derived start treatment start date in ARQ-154-214 – last treatment date in ARQ-154-203 + 1.
- **Treatment Duration (weeks)** = (last date of IP application – first date of IP application +1)/7.
- **Duration of IGA success** = The date of first observation where IGA does not meet success criteria - the date of first observation of IGA success + 1. The duration of IGA success for subjects who end treatment in IGA success will be censored at the last disease assessment date. Only the first duration of IGA success will be analyzed.

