7.6. Exposure and Compliance

The number of IP applications by each subject based on diary data will be summarized using descriptive statistics appropriate for continuous variables.

The amount of IP used by each subject based on can weight will be summarized descriptively using continuous methods.

The number of days on IP will be derived as indicated in Section [6.1.7](#) and summarized descriptively.

The gap between completing study ARQ-151-203 and enrolling into this study will not be included in the above definition and will be summarized separately for subjects in Cohort 2 Group 3.

A subject will be considered compliant with the dosing regimen if the subject applies at least 80% of the expected applications during the IP application period and does not miss more than 3 consecutive doses. Doses missed due to IGA clearance were not considered as noncompliance.

AD-ST-33.06 Effective date: 12-Nov-2020

The number and percent of subjects that missed more than 3 consecutive doses will be tabulated except for subjects who withheld IP application due to IGA clear per investigator.

Investigational product application compliance will be calculated based on number of applications divided by the expected number of IP applications. Compliance will be summarized descriptively using the following categories:

- > 100%
- $\geq 80\% - \leq 100\%$
- < 80%

Drug exposure and compliance will be presented using primary and OLE baselines. The number of subjects with treatment duration (≥ 1 day, ≥ 8 weeks, ≥ 12 weeks, ≥ 24 weeks, ≥ 32 weeks, ≥ 54 weeks, and ≥ 62 weeks) will also be summarized similarly. Study duration will be summarized from primary and OLE baseline.

Similar exposure and compliance information will be summarized for subjects who completed or discontinued study before protocol amendment 1.

8. Efficacy Analysis

This study is open label without a comparator group; therefore, there will be no formal hypothesis testing performed in the study.

For the continuous variables, the number of nonmissing values and the mean, SD, minimum, Q1, Q3, median, and maximum will be tabulated by study visit; similarly, categorical variables will have the counts and proportions of each value will be tabulated by study visit.

For efficacy summaries 2 baselines will be used (primary and OLE) using Safety population as defined in Section [6.1.1](#).

All efficacy summaries for primary and OLE baselines will be presented as indicated below:

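### SAP 8.3 limits six baseline-dependent secondary endpoints to the OLE baseline, against SAP 6.1.1 and Section 8 and, for five of them in Cohort 1, against Protocol 7.1.1

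*SAP*

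**What the plan says.** SAP 8.3 sets the baseline for the other secondary efficacy endpoints: "The other secondary efficacy endpoints are summarized using OLE baseline, except for WI-NRS which will be summarized at both primary and OLE baseline". Its next sentence sends the reader back to the general efficacy section: "These are summarized as discussed in Section 8 and include the following".

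SAP Section 8 gives the general rule: "For efficacy summaries 2 baselines will be used (primary and OLE) using Safety population", and then "All efficacy summaries for primary and OLE baselines will be presented as indicated below". The baseline table in SAP 6.1.1 enters "Primary baseline and OLE baseline" under efficacy in every row, from Cohort 1 Group 1 to Overall. SAP 6.1.7 derives change and percent change separately for each baseline.

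Protocol 7.1.1 defines the Cohort 1 baseline for safety and efficacy as "the last observation prior to the first dose of ARQ-154 foam 0.3% in either the prior ARQ-154 study or this study". It adds the baseline from this study as an additional analysis. For Cohort 2 it uses the last observation before the first dose in this study. Protocol 7.3.2 analyses Scalpdex as change from Day 1.

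SAP 6.1.7 also restricts the erythema success table: "the subjects who achieved erythema score of 0 or 1 at baseline will be excluded from the analysis". Scaling success carries the same restriction. SAP 10, which lists changes from the planned analysis, does not mention baselines.

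**The concern.** The SAP gives two instructions for the same tables. Section 8 calls for two versions and 8.3 calls for one. For Cohort 1, the one kept is the version that the protocol treats as additional, and the main version is dropped without being recorded.

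The choice matters because OLE baseline is not a pre-treatment value for everyone. A subject who received roflumilast in ARQ-154-203 has already been exposed by then. Change from that point leaves out whatever was gained in the parent study, and the success tables leave out subjects who had reached 0 or 1. Vehicle rollovers and de novo subjects are measured from a value before any roflumilast. A total column therefore averages two kinds of change.

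**Working it through.** The plan gives no figure to reproduce on this point. The check is a comparison of texts, a count, and two illustrations.

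**1. Endpoints affected.** SAP 8.3 lists 11 endpoints. Three are WI-NRS endpoints and keep both baselines, which leaves 11 − 3 = 8 on OLE baseline only (8/11 = 73%). Two of the eight, erythema score of 0 and scaling score of 0, do not use a baseline. That leaves 8 − 2 = 6: change in Scalpdex, erythema, scaling and BSA, erythema success, and scaling success.

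**2. Conflict by cohort.**
- *Within the SAP.* Sections 6.1.1 and 8 require both baselines and 8.3 allows one, so all six endpoints conflict in both cohorts.
- *Against the protocol, Cohort 1.* Protocol 7.1.1 makes the value before the first active dose the main one. Footnote l to the schedule in Protocol 1.3 also places the efficacy baseline at Day 1 of the prior study. Protocol 7.3.2 takes Scalpdex from Day 1, and Protocol 5.3 makes Day 1 for Cohort 1 the final visit of the preceding study, which is the OLE baseline. That leaves 6 − 1 = 5 endpoints in conflict.
- *Against the protocol, Cohort 2.* No conflict, because Protocol 7.1.1 uses the baseline from this study.

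**3. Subjects affected.** SAP Section 8 notes that the two baselines coincide for vehicle rollovers and de novo subjects. The difference therefore falls on prior-roflumilast subjects in Groups 1 and 3, and on the Group 1 Total, Group 3 Total, Cohort 2 Total and Overall columns.

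**4. Success tables.** Success means a score of 0 or 1 plus a 2-grade improvement. Take erythema on the 0–3 scale and assume a primary baseline P of 2 or 3. Success from P requires (P, visit) = (2, 0), (3, 0) or (3, 1). With four possible OLE scores, that gives 3 × 4 = 12 trajectories. Under OLE baseline:
- OLE score 0 or 1: 3 × 2 = 6 are excluded.
- OLE score 2: (2, 0) and (3, 0) remain successes, and (3, 1) becomes a failure because 2 − 1 = 1 grade.
- OLE score 3: all 3 remain successes.

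Of the 12, then, 6 are excluded, 1 fails and 5 stay. One trajectory goes the other way: 2, then 3, then 1 succeeds only from OLE baseline. These are counts of possible paths, not of subjects.

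The SAP expects subjects to be clear or nearly clear at OLE baseline. Its IGA subgroups in 6.1.6 are 3 and 4 at primary baseline but include 0 or 1 at OLE baseline. By SAP Table 4, IGA 0 means no erythema and no scaling. Such subjects leave both success tables, and their percent change in these scores is undefined because the formula in 6.1.7 divides by baseline.

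**5. Illustrative size (assumed values; the documents give none).** Take a prior-roflumilast mean erythema of 2.2 at primary baseline and 0.6 at a visit in this study. Change from primary is 0.6 − 2.2 = −1.6.
- OLE mean 0.6: change is 0.6 − 0.6 = 0.0, or 0% of −1.6.
- OLE mean 1.0: change is 0.6 − 1.0 = −0.4, or 25%.
- OLE mean 1.6: change is 0.6 − 1.6 = −1.0, or 62.5%.

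If 30% to 70% of these subjects are at 0 or 1 at OLE baseline, the success denominator is 70 down to 30 per 100.

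**6. Is the missing version ready to run?** SAP Table 2 gives primary-baseline visit windows for prior-roflumilast subjects. Its OLE-visit targets equal the Table 3 targets plus the 56 days of ARQ-154-203: 29 + 56 = 85, 85 + 56 = 141, 169 + 56 = 225, 253 + 56 = 309, 365 + 56 = 421. No new windows or derivations are needed.

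**The case against.** The best defence is that 8.3 is a specific rule. It names its one exception, so it looks deliberate, and a programmer following it would know which tables to produce. OLE baseline also answers a fair question, namely what further change occurred in this study. For Scalpdex and for Cohort 2 it is the baseline that the protocol itself uses. Group 3 entered after a treatment gap, so its OLE baseline is not an on-treatment value.

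The loss of information is also partial. SAP 7.2 presents erythema, scaling, Scalpdex, WI-NRS and BSA at both baselines. SAP 8.3 still reports observed Scalpdex and BSA values, erythema and scaling categories, and score-of-0 rates. IGA and WI-NRS are summarised from both baselines. None of the six endpoints is among the secondary endpoints of Protocol 4.2.2, and SAP 6.1.2 plans no inferential analysis.

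Most of this stands and limits the size of the point. The specific-rule argument does not remove it. Sections 6.1.1 and 8 contain no exception, 8.3 refers back to Section 8, and even a deliberate exception would replace the main Cohort 1 baseline of Protocol 7.1.1 with no entry in SAP 10. Levels at two baselines also do not give within-subject change or success from the primary one.

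**Conclusion.** The inconsistency is real and worth correcting, with modest consequence. Six of 11 endpoints lose a primary-baseline summary that SAP 6.1.1 and Section 8 require. For five of them, in Cohort 1, the SAP also departs from Protocol 7.1.1 without recording it. For prior-roflumilast subjects, improvement from ARQ-154-203 is left out of the change scores, those at 0 or 1 are dropped from the success tables, and the total columns mix baselines taken before and after roflumilast. How large this is depends on the scores at rollover, which the documents do not give. The primary safety endpoints are untouched.

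A reader might infer more, and the documents do not support it:
- *That the effect is hidden.* Levels at both baselines, observed values and category counts remain on display.
- *That only parent-study non-responders stay in the success tables.* A subject who improved from 3 to 2 stays in, as would a Group 3 subject who relapsed to 2 or 3 during the gap.
- *That change will be near zero for all prior-roflumilast rollovers.* Group 3 starts off treatment, and no rollover scores are given for Group 1.
- *That the protocol is contradicted throughout.* It is not for Cohort 2, nor for Scalpdex.

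**What to change.** In SAP 8.3, summarise change in erythema, scaling and BSA, and erythema and scaling success, from both primary and OLE baseline. Make primary baseline the main presentation for Cohort 1 Group 1, as in Protocol 7.1.1. For Cohort 2 the baseline from this study can remain the main one. For Scalpdex, keep change from Day 1 as in Protocol 7.3.2 and add change from primary baseline as a further summary.

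If the restriction is intended, the alternative is to write the exception into SAP 6.1.1 and Section 8, and to record and justify it in SAP 10.

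The cost of the preferred change is a few lines of SAP text and a second run of existing tables. It needs no new data, visit windows or derivations, and no change to the sample size.

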9.1. Adverse Events

All AEs will be coded using the MedDRA dictionary version 24.1 or above.

A TEAE is defined as an AE that started after application of IP at the Baseline Visit in this extension study. All TEAEs will be summarized from OLE baseline.

An overall summary of TEAEs will be provided; this will present number and percent of subjects who reported at least 1: TEAE (including all TEAEs, TEAEs by maximum severity, and TEAEs by greatest relationship), treatment emergent SAE (TESAE), TEAE leading to study drug withdrawal, TEAE leading to study withdrawal, or TEAE resulting in death.

The number and percent of subjects reporting TEAEs, grouped by MedDRA system organ class (SOC) and preferred term (PT), will be tabulated by all TEAEs, non-serious TEAEs, maximum severity, or greatest relationship to study IP; Cohort and by groups and overall. In the case of multiple occurrences of the same TEAE within the same subject, each subject will only be counted once for each preferred term.

The number and percent of subjects reporting TEAEs will be tabulated by PT and presented by groups and overall.

In the summaries showing severity and relationship to study medication, the event with the maximum severity (mild < moderate < severe) or strongest relationship (not related < related) will be reported. If a particular event is missing the severity and/or relationship, then the strongest possible severity or relationship will be assumed for analysis (severity = severe, relationship = likely).

All the AEs will be listed. The AEs that are treatment emergent will be flagged. Any AEs related to the application site will be flagged in the listing.

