4.2. Study Endpoints

4.2.1. Primary Endpoints

The primary endpoint will be analysis of safety monitored through application site assessments in the clinic using the method of Berger and Bowman, clinical laboratory testing, PHQ-8, Modified PHQ-A, CDI-2, C-SSRS and adverse events. Two primary endpoint analyses are planned:

- Occurrence of treatment emergent AEs (TEAEs)
- Occurrence of Serious Adverse Events (SAEs)

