5.4.3. Removal of Subjects from Investigational Product

A subject may discontinue from receiving the investigational product for any of the following reasons:

- Occurrence of any medical condition or circumstance that, in the opinion of the Investigator, exposes the subject to substantial risk and/or does not allow the subject to adhere to the requirements for investigational product administration as per the protocol.
- Occurrence of a treatment-emergent adverse event (TEAE) or considerable worsening of an AE that, in the opinion of the Investigator in consultation with the Medical Monitor and Sponsor, represents an unacceptable risk to the subject if he/she continues in the study. The Investigator must follow the subject until the AE resolves or satisfactorily stabilizes.
- Pregnancy.
- Subject's decision to withdraw from administration of the investigational product.
- Weight loss of >5% from Baseline if not dieting or intentionally trying to lose weight and after consultation with the Sponsor, at the Investigator's discretion.
- C-SSRS indicative of suicidal ideation.
- PHQ-8 or modified PHQ-A score ≥ 15 if determined by Investigator in consultation with a mental health professional.
- CDI-2 raw score of ≥ 32 if determined by Investigator in consultation with a mental health professional.
- Requirement for use of prohibited concomitant medication (see [Table 1](#)) after consultation with the Sponsor and Medical Monitor.
- Subject's repeated failure to comply with protocol requirements or study related procedures.

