6.6. Adverse Events

6.6.1. Adverse Event Definition

An AE means any untoward medical occurrence associated with the use of a drug in humans, whether or not considered drug related. An AE can therefore be any unfavorable and unintended sign (including an abnormal laboratory finding), symptom, or disease temporally associated with the use of a medicinal (investigational) product, whether or not related to the medicinal (investigational) product.

AEs will be collected following informed consent of the subject through subject study completion.

A treatment emergent adverse event (TEAE) is defined as an AE that started post application of IP at the Day 1 visit through study completion.

Application site reactions will be considered adverse events if they require intervention, suspension or discontinuation of IP.

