6.6.5. Adverse Event Reporting

The Investigator will review each event and assess its relationship to drug treatment (unrelated, unlikely, possibly, probably, likely). Each sign or symptom reported will be graded on the most current version of the NIH NCI CTCAE toxicity grading scale 5-point severity scale (Grade 1, 2, 3, 4 and 5). The date and time of onset, time relationship to drug dosing, duration, and outcome of each event will be noted.

The relationship of each AE to the IP will be assessed using the following definitions:

Unrelated	
• The AE must clearly be caused by the subject's clinical state, or the study procedure/conditions.• Definitely not related to drug.• Temporal sequence of an AE onset relative to administration of drug not reasonable.• Another obvious cause of an AE.
Unlikely	
• Time sequence is unreasonable.• There is another more likely cause for an AE.
Possibly	
• Corresponds to what is known about the drug.• Time sequence is reasonable.• Could have been due to another equally, likely cause.
Probably	
• Is a known effect of the drug.• Time sequence from taking drug is reasonable.• Ceases on stopping the drug.• Cannot be reasonably explained by the known characteristics of the subject's clinical state.
Likely	
• Is a known effect of the drug (e.g., listed in Physicians' Desk Reference, Compendium of Pharmaceuticals and Specialties, IB).• Time sequence from taking drug is reasonable.• Event stops upon stopping drug, event returns upon restarting drug.

The following CTCAE toxicity grading scale 5-point severity scale definitions for rating maximum severity will be used:

Grade 1	Mild; asymptomatic or mild symptoms; clinical or diagnostic observations only; intervention not indicated.
Grade 2	Moderate; minimal, local or noninvasive intervention indicated; limiting age-appropriate instrumental activities of daily living.*
Grade 3	Severe or medically significant but not immediately life-threatening; Hospitalization or prolongation of hospitalization indicated; disabling; limiting self-care activities of daily living.** Note: An experience may be severe but may not be serious, e.g., severe headache).
Grade 4	Life-threatening consequences; urgent intervention indicated.
Grade 5	Death related to AE.

Note: A semi-colon indicates 'or' within the description of the grade.

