- **TEAE** = any AE that started after application of IP at the Baseline Visit in this extension study, or in parent study through completion.
- **C-SSRS Suicidal Ideation** = A “yes” answer at any time during treatment to any one of the five suicidal ideation questions (Categories 1-5: Wish to be Dead, Non-specific Active Suicidal Thoughts, Active Suicidal Ideation with Any Methods (Not Plan) without Intent to Act, Active Suicidal Ideation with Some Intent to Act, without Specific Plan Active Suicidal Ideation with Specific Plan and Intent).
- **C-SSRS Suicidal Behavior** = A “yes” answer at any time during treatment to any one of the five suicidal behavior questions (Categories 6-10: Preparatory Acts or Behavior, Aborted Attempt, Interrupted Attempt, Actual Attempt (non-fatal), Completed Suicide).

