6.1.8. Data Adjustments/Handling/Conventions

All collected data will be presented in Clinical Data Interchange Standards Consortium (CDISC) datasets. Data not subject to analysis according to this plan will not appear in any tables or graphs but will be included only in the CDISC datasets.

All *P* values will be displayed in four decimals and rounded using standard scientific notation (eg, 0.XXXX). If a *P* value less than 0.0001 occurs it will be shown in tables as <0.0001; similarly, if a *P* value greater than 0.9999 occurs it will be shown in tables as >0.9999.

Adverse events will be coded using the MedDRA version 24.1 thesaurus. Medications will be coded using the World Health Organization Drug Dictionary Enhanced (WHO-DDE) Global B3 version September 2021.

A treatment-related AE is any AE with a relationship to the study drug of possibly related, probably related, likely related, or missing.

For partial AE and medication start dates:

- If the year is unknown, then do not impute the date but assign a missing value.
- If the year is known, but the month or month and day is unknown, then:
 - If the year matches the year of first dose date and the end date (if present) is after first dose date, then impute as the month and day of the first dose date.
 - Otherwise, assign 01 January.
- If the year and month are known, but the day is unknown, then:
 - If the month and year match the month and year of the first dose date, then impute as the day of the first dose date.
 - Otherwise, assign 01.

For partial AE and medication end dates:

- If the year is unknown, then do not impute the date but assign as missing value.
- If the year is known, but the month or month and day is unknown, then:
 - If the year matches the year of the last date of the study (date of last contact if subject lost to follow-up; date of completion or early termination otherwise), then impute as the month and day of the last date of the study.
 - Otherwise, assign 31 December.
- If the year and month are known, but the day is unknown, then:
 - If the month and year match the month and year of the last date of the study, then impute as the day of the last date of the study.
 - Otherwise, assign the last day of the month.

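### TEAE occurrence, one of two primary endpoints, is defined by onset alone and inconsistently across four sections, and one branch of the partial-date rule can give an AE that ended before dosing a first-dose-day start.

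*SAP*

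**What the plan says.** Protocol 4.2.1 and SAP 2.2.2 name two primary endpoint analyses: occurrence of TEAEs and occurrence of SAEs. A TEAE is defined in four places:

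- Protocol 6.6.1: a TEAE "is defined as an AE that started post application of IP at the Day 1 visit through study completion".
- Protocol 7.2.1: onset on the first treatment date in this study, or later.
- SAP 6.1.7: "any AE that started after application of IP at the Baseline Visit in this extension study, or in parent study through completion".
- SAP 9.1: "A TEAE is defined as an AE that started after application of IP at the Baseline Visit in this extension study".

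None has a clause for worsening. Protocol 5.4.3 nevertheless separates the two ideas in its reasons for stopping IP: "Occurrence of a treatment-emergent adverse event (TEAE) or considerable worsening of an AE that, in the opinion of the Investigator". Protocol 6.6.5 introduces its CTCAE grades with "definitions for rating maximum severity will be used". Neither document says that a rise in grade opens a new AE record.

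SAP 6.1.8 handles partial start dates in two relevant branches. With the month unknown, the first-dose date is imputed under the condition "If the year matches the year of first dose date and the end date (if present) is after first dose date"; otherwise the date is set to 01 January. With only the day unknown, the condition is just "If the month and year match the month and year of the first dose date", and the first-dose day is then imputed.

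AEs are collected from informed consent (Protocol 6.1.10). Cohort 2 consents at screening, up to 35 days before Day 1. Cohort 1 consents after the parent study's final visit, which serves as its Day 1 (Protocol 1.3, footnote k).

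**The concern.** An onset-only definition does not count deterioration on drug of something already present. This design makes that case likely enough to matter. Cohort 1 moves from the parent study into this one on the same day, so ongoing AEs carry straight into dosing. Group 1 includes parent-study vehicle subjects, whose first active exposure is here. An event that began on vehicle and worsens on roflumilast is not a TEAE under Protocol 6.6.1, Protocol 7.2.1 or SAP 9.1. The SAP's SAE tables (9.1.2) and withdrawal tables (9.1.1) are limited to treatment-emergent events, so the same subject is missing from those counts as well.

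The partial-date branch works in the opposite direction. It can add to the TEAE count an event that was over before the first application in this study.

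**Working it through.** **Definitions side by side.** Would each definition count the event as a TEAE?

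| Definition | Starts in Cohort 2 screening, worsens on drug | Starts after IP in the parent study, worsens here | Start imputed to the first-dose day |
|---|---|---|---|
| Protocol 6.6.1 | No | No | Undetermined |
| Protocol 7.2.1 | No | No | Yes |
| SAP 6.1.7 | No | Yes, on its wording | Undetermined |
| SAP 9.1 | No | No | Undetermined |

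The first column shows the worsening gap, the second the contradiction, and the third the boundary problem. An imputed date carries no time of day, so a rule that requires onset after application cannot classify it.

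**SAP 6.1.8 applied by hand.** Take a first dose in this study on 20 June 2021.

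1. Start June 2021 with the day missing, end 10 June: the start is imputed as 20 June, which is 20 − 10 = 10 days after the event ended. It is a TEAE under Protocol 7.2.1.
2. Start 2021 with month and day missing, end 10 June: the end-date check sends it to 01 January. It is not a TEAE.
3. Start May 2021 with the day missing, end 30 May: imputed as 01 May. It is not a TEAE.

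Record 1 carries more information than record 2 and gets the worse answer.

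**Share of day-unknown, pre-dose AEs exposed.** Inputs: the 35-day screening window (Protocol 6.1), and first-dose dates spread evenly over a 365-day year (an assumption).

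- *One-day events, evenly spread over the window.* A first dose on day d of a month leaves d − 1 earlier days in that month. For a month of n days these sum to n(n − 1)/2, which is 465, 435 or 378 for 31, 30 or 28 days. The mean is (7 × 465 + 4 × 435 + 378)/365 = 5,373/365 = 14.7 days, and 14.7/35 = 42%.
- *Every start and end pair before first dose.* There are 35 × 36/2 = 630 pairs per first-dose date, and 630 × 365 = 229,950 in all. Pairs starting in the first-dose month number d(d − 1)/2 for first-dose day d. These sum to (n + 1)n(n − 1)/6 per month, which is 4,960, 4,495 or 3,654. The total is 7 × 4,960 + 4 × 4,495 + 3,654 = 56,354, and 56,354/229,950 = 24.5%.

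All 56,354 pairs get a start later than their end. All are TEAEs if the first-dose date counts, and none is under a strictly-later date comparison. The month-unknown branch converts 0 pairs under either reading.

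**With the end-date check added to the day-unknown branch,** the count falls to 0. An event that starts in the first-dose month and ends before first dose is set to day 01, which is no later than its end and so before dosing.

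**Effect per subject.** 1/400 = 0.25 percentage points on the TEAE proportion.

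**The case against.** The best reply is that little is hidden. SAP 9.1 lists all AEs, treatment-emergent or not. Protocol 7.2.1 also lists subjects who stop IP because of an AE, without a TEAE restriction. The risks known from oral roflumilast have analyses that do not depend on onset: 5% and 10% weight shifts (from the pre-active baseline for Cohort 1 Group 1), PHQ-8 and PHQ-A shift tables, CDI-2 summaries and C-SSRS tables. CRF completion rules, which are not in the documents, might already require a new record when an AE worsens. Protocol 6.6.5 asks for date and time of onset, so missing days may be rare. All of this stands. It confines the point to the TEAE-based tables, but those carry a primary endpoint.

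Several stronger readings are tempting but not supported:

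- *A parent-study onset that worsens contributes no TEAE.* SAP 6.1.7 counts parent-study onsets, so the status is contradictory, not zero.
- *Both primary endpoints are biased down.* The protocol's SAE endpoint is not limited to treatment-emergent events; only the SAP's SAE tables are.
- *The partial-date rule as a whole is faulty.* Only the day-unknown, same-month branch lacks the check.
- *Washed-out medications become concomitant.* The medication's start must also fall in the first-dose month with its day missing. With a 4-week washout that needs a first dose on about day 29 or later; with 12 weeks it cannot happen.

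Reading SAP 9.1 strictly does not rescue the plan. If an imputed first-dose-day start is never a TEAE, then an AE starting in June with the day missing and ending on 25 June, after a first dose on 20 June, is also excluded, although it may have begun on drug.

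**Conclusion.** Both defects are in the text. Three of the four definitions fail to count any pre-dose AE that worsens or becomes serious on drug. The fourth, SAP 6.1.7, fails for screening onsets and conflicts with SAP 9.1 on parent-study onsets. The day-unknown branch of SAP 6.1.8 creates starts later than ends; these are TEAEs under Protocol 7.2.1 and undetermined under SAP 9.1.

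The partial-date problem falls mainly on Cohort 2, the cohort with a pre-dose collection window. It assumes that the first-dose date in SAP 6.1.8 means first dose in this study. The 42% and 24.5% are shares of day-unknown, pre-dose AEs under two uniform patterns. They should not be read as expected study rates. The number of partial-date and worsening records is not given, so neither the size nor the net direction of the effect on the TEAE rate can be stated. The study is descriptive, so no test is affected; what is at stake is whether the primary TEAE count is well defined.

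**What to change.** 1. In SAP 6.1.8, when only the day is missing and the month is that of first dose, impute the first-dose day only if the end date is missing or is on or after first dose. Otherwise impute day 01.
2. Use one TEAE definition in Protocol 6.6.1 and 7.2.1 and SAP 6.1.7 and 9.1: onset on or after first IP in this study, counting starts imputed to the first-dose day; or earlier onset with an increase in severity grade, or becoming serious, after first IP. Have sites record the worsening with its date.
3. Remove the parent-study clause from SAP 6.1.7 or reconcile it with SAP 9.1.

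The cost is SAP wording, minor programming and one CRF completion instruction. The protocol sections need an amendment, with IRB approval under Protocol 8.6. TEAE counts may rise slightly from the worsening clause and fall slightly from the end-date check.
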